## **4.2 Exclusion Criteria**

**4.2.1** The presence of known lung, liver, or brain metastases, malignant pleural effusions, or malignant ascites. In the case of suspected or questionable findings, the investigator must assess and document each finding in the subject's medical record prior to registration.

**4.2.2** Spinal cord compression, imminent long bone fracture, or any other condition that, in the opinion of the investigator, is likely to require radiation therapy and/or steroids for pain control during the active phase.

**4.2.3** History of stage 3 or greater cancer, excluding prostate cancer. Basal or squamous cell skin cancers must have been adequately treated and the subject must be disease free at the time of registration. Subjects with a history of stage 1 or 2 cancer must have been adequately treated and been disease free for  $\geq 3$  years at the time of registration.

**4.2.4** History of seizures or of predisposing factors for seizures, including underlying brain injury with loss of consciousness within previous 12 months, transient ischemic attack within previous 12 months, cerebral vascular accident or brain arteriovenous malformation.

**4.2.5** Child-Pugh Class C hepatic insufficiency (see [Appendix 2](#)).

**4.2.6** History of allergic reactions attributed to compounds of similar chemical or biologic composition to sipuleucel-T, GM-CSF or granulocyte colony stimulating factor (G-CSF).

**4.2.7** Previous treatment with sipuleucel-T or enrollment in a sipuleucel-T trial, regardless of whether the subject received sipuleucel-T or control.

**4.2.8** Previous treatment with enzalutamide.

**4.2.9** Previous treatment with abiraterone acetate.

**4.2.10** Previous treatment with ipilimumab.

**4.2.11** Previous treatment with ketoconazole other than topical use or for treatment of infections (e.g., oral thrush); most recent use must have been  $\geq$  7 days prior to registration.

**4.2.12** Previous treatment with any immunotherapy or investigational vaccine.

**4.2.13** A requirement for ongoing systemic immunosuppressive therapy. Use of inhaled, intranasal, intra-articular, and topical steroids is allowed. Oral or IV steroids to prevent or treat IV contrast reactions are allowed.

**4.2.14** Previous treatment with chemotherapy for mCRPC, or chemotherapy for any reason  $\leq$  2 years prior to registration.

**4.2.15** Use of concomitant medications that may lower the seizure threshold or the use of antiseizure medications  $\leq$  1 year prior to registration.

**4.2.16** Received GM-CSF or G-CSF  $\leq$  90 days prior to registration.

**4.2.17** Ongoing non-steroidal antiandrogen withdrawal response. Subjects on combined androgen blockade with a non-steroidal antiandrogen and LHRH agonist must discontinue the non-steroidal antiandrogen. A PSA level must be obtained  $<$  28 days prior to the antiandrogen discontinuation and then again  $>$  28 days following discontinuation. If the PSA has dropped  $>$  25% from the time of antiandrogen discontinuation, subjects are not eligible until the PSA rises above the post-antiandrogen discontinuation nadir.

**4.2.18** Any of the following medications or interventions  $\leq$  28 days prior to registration:

- Radiation therapy, either via external beam or brachytherapy.
- Any systemic steroid. Use of inhaled, intra-nasal, intra-articular, and topical steroids is allowed. Oral or IV steroids to prevent or treat IV contrast reactions are allowed.

- Any systemic therapy for prostate cancer, except for ADT.
- Any investigational product for prostate cancer.
- Major surgery requiring general anesthesia, with the exception of placement of central venous catheters.
- Inducers and inhibitors of cytochrome P450 (CYP) enzyme CYP2C8 (gemfibrozil and rifampin [see [Appendix 3](#)]).
- Medications that are metabolized by CYP3A4, CYP2C9, or CYP2C19 that have a narrow therapeutic index (see [Appendix 3](#)).
- Inducers of CYP3A4 (including but not limited to phenytoin, carbamazepine, rifampin, rifabutin, rifapentine, and phenobarbital [see [Appendix 3](#)]).

**4.2.19** A requirement for treatment with opioid analgesics for cancer-related pain  $\leq$  21 days prior to registration.

**4.2.20** An active infection requiring parenteral antibiotic therapy or causing fever (temperature  $> 100.5^{\circ}$  F or  $38.1^{\circ}$  C)  $\leq$  1 week prior to registration.

**4.2.21** Any medical intervention, any other condition, or any other circumstance which, in the opinion of the investigator or the Dendreon medical monitor, could compromise adherence with study requirements or otherwise compromise the study's objectives.

### **4.3 Discontinuation from Study Treatments or Assessments**

The investigator may withdraw a subject from one or both study treatments, or from study assessment, if, in his or her clinical judgment, it is in the best interest of the subject.

#### **4.3.1 Discontinuation from Sipuleucel-T Treatment**

Subjects who have received at least 1 partial ( $> 0$  mL) infusion of sipuleucel-T may discontinue sipuleucel-T without the requirement to discontinue enzalutamide, provided the criteria for removal from all study treatments (see [Section 4.3.3](#)) have not been met. These subjects will continue all protocol-specified assessments in the active phase.

Any toxicity requiring sipuleucel-T discontinuation will be recorded as an AE in the subject's medical record and on the case report form (CRF).

#### **4.3.2 Discontinuation from Enzalutamide Treatment**

Dose reduction for enzalutamide will not be permitted and subjects with any toxicity requiring enzalutamide dose reduction must discontinue enzalutamide treatment.

Subjects who have not received 3 sipuleucel-T infusions may discontinue enzalutamide treatment without the requirement to discontinue sipuleucel-T provided the criteria for removal from all study treatments (Section 4.3.3) have not been met. These subjects will undergo a post-treatment visit after the last sipuleucel-T infusion and enter the LTFU phase.

Subjects who have already received 3 sipuleucel-T infusions and  $\geq$  10 weeks of enzalutamide treatment when they discontinue enzalutamide will continue all protocol-specified assessments in the active phase. Subjects who have received less than 10 weeks of enzalutamide treatment when they discontinue enzalutamide will undergo a post-treatment visit and enter the LTFU phase.

Any toxicity requiring enzalutamide discontinuation or dose reduction will be recorded as an AE in the subject's medical record and on the CRF.

#### **4.3.3 Discontinuation from All Study Treatments**

Subjects will discontinue from all study treatments, undergo a post-treatment visit, and enter the LTFU phase for any of the following reasons:

- The subject withdraws consent to receive study treatments.
- The subject is unable to, or refuses to, undergo leukapheresis.
- The subject is unable to, or refuses to, receive at least 1 partial ( $> 0$  mL) sipuleucel-T infusion.
- Dendreon is unable to manufacture sipuleucel-T for the subject.
- The subject develops disease progression as defined in Section 4.5.
- The subject develops any condition requiring a prohibited treatment (see Section 4.7).
- Treatment is stopped at the discretion of the investigator or Dendreon.

#### **4.3.4 Discontinuation from the Study**

Subjects may discontinue their participation in the trial at any time without prejudice. If a subject withdraws consent for any further study involvement, complete withdrawal of consent must be documented in the subject's medical record. The date and reason for withdrawal will be recorded in the subject's medical record and on the CRF.

Whenever possible, subjects discontinuing from the study will undergo a post-treatment visit. All AEs considered by the investigator to be related to study treatment(s) that are ongoing at the time of discontinuation will be followed by the investigator until resolution or until the subject returns to baseline. The investigator should make every reasonable attempt to ensure that the subject is contacted (via telephone or during a post-treatment visit) to obtain the final status of any AEs and concomitant medications.

Subjects will discontinue from the study (all treatment and subsequent assessments) for any of the following reasons:

- The subject withdraws consent for any reason.
- The subject loses the ability to freely provide consent.
- The subject is lost to follow-up.
- The subject fails to comply with protocol requirements.
- The subject is discontinued from the study at the discretion of the investigator or Dendreon.
- Dendreon terminates the study.

Subjects who withdraw consent, or lose the ability to freely provide consent, will be followed by the investigator for survival every 3 months using the Social Security Death Index (SSDI) and National Death Index (NDI). Date of death, where available, will be recorded in the subject's medical record and on the CRF.

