#### **4.4 Lost to Follow-Up**

If the subject fails to respond to requests for follow-up, the clinical trial site will send a registered letter, at a minimum, to the subject requesting contact with the clinic. All attempts to resume contact (including copies of written correspondence) will be included in the source documentation. Subjects who do not respond to requests for follow-up after all reasonable attempts to establish contact will be considered "lost to follow-up". Subjects who are lost to

follow-up will be followed by the investigator for survival every 3 months using the SSDI and the NDI. Date of death, where available, will be recorded in the subject's medical record and on the CRF.

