## **8.3 Populations for Analyses**

The immune response population will be defined as subjects who receive 3 infusions of sipuleucel-T and 10 or more weeks of enzalutamide. Analysis of immune response endpoints, including the primary endpoint, will be performed using this population. This population will also be used to perform supplementary analyses of nonimmune response efficacy endpoints.

The intent-to-treat (ITT) population is defined as all randomized subjects, regardless of whether they received treatment. Analysis of nonimmune response efficacy endpoints will be performed using this analysis population.

The safety population will include all subjects who receive at least 1 leukapheresis procedure or receive at least 1 dose of enzalutamide. All safety variables (e.g., AEs, laboratory data, and vital sign data) will be analyzed based on the safety population.

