#### **8.4.2 Secondary Endpoint(s)**

Immune responses over time for ELISPOT and ELISA are secondary endpoints as are peripheral PAP-specific T cell immune response to sipuleucel-T over time via a T cell stimulation index from a proliferation assay, and cytokine production by Luminex assay. Additionally, responder analyses by time point will be performed for the data generated from the proliferation assays, ELISPOT, and ELISA. A positive response will be defined as having a post-baseline result exceeding a threshold value, determined on the basis of baseline and historical sipuleucel-T data, that ensures a sufficiently low false positive rate (i.e., 5% or less) for each immune response parameter. The threshold will be antigen and assay dependent.

Time to PSA progression is defined as: 1) the time from randomization to PSA progression, and 2) the time from first enzalutamide treatment to PSA progression. Those subjects who do not experience PSA progression will be censored in the analysis at the date of their last PSA assessment. PSA progression, based on the randomization date (i.e., definition 1) will be defined for those subjects who experience a decline in PSA compared to baseline as the date that a 25% or greater increase in PSA and an absolute increase of 2 ng/mL or more from the nadir is documented, which is confirmed by a second value obtained 3 or more weeks later (Scher 2008). For those subjects who do not experience a decline in PSA compared to baseline, PSA progression is defined as the date a 25% or greater increase from the baseline value along with an increase in absolute value of 2 ng/mL or more after 12 weeks of enzalutamide treatment (Scher 2008). PSA progression based on the first enzalutamide treatment (i.e., definition 2) will be defined in a similar manner except the most recent PSA value prior to the first enzalutamide treatment will be used as the baseline value.

PSA progression time, based on the randomization date, will be calculated as follows for those subjects with PSA progression:

$$\text{Progression time (days)} = [(\text{PSA progression date}) - (\text{randomization date})] + 1.$$

PSA progression time, based on the randomization date, will be calculated as follows for subjects who are censored:

$$\text{PSA progression time (days)} = [\text{last PSA assessment date} - (\text{randomization date})] + 1.$$

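### Men removed from the study for non-compliance or at investigator or sponsor discretion get no death-index tracing under Protocol 4.3.4 and 4.4, so they are censored early for overall survival although they remain in the ITT set.

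*Protocol*

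**What the plan says.** Protocol 4.3.4 opens its list of study exits with "Subjects will discontinue from the study (all treatment and subsequent assessments) for any of the following reasons". The list includes "The subject fails to comply with protocol requirements" and "The subject is discontinued from the study at the discretion of the investigator or Dendreon". Neither reason carries a threshold or criteria.

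The same section then provides survival tracing through the Social Security Death Index and National Death Index (SSDI/NDI) for two groups: "Subjects who withdraw consent, or lose the ability to freely provide consent, will be followed by the investigator for survival every 3 months". Protocol 4.4 adds a third: men lost to "follow-up will be followed by the investigator for survival every 3 months using the SSDI and the NDI". Neither section names men removed for non-compliance or at discretion.

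Stopping treatment alone is handled differently. Protocol 4.3.3 says "Subjects will discontinue from all study treatments, undergo a post-treatment visit, and enter the LTFU phase for any of the following reasons", and that list already contains a discretionary stop by the investigator or sponsor. Long-term follow-up (LTFU) then continues.

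On analysis, Protocol 8.3 states: "The intent-to-treat (ITT) population is defined as all randomized subjects, regardless of whether they received treatment". This population is used for overall survival and the other non-immune efficacy endpoints. Under Protocol 8.4.2 and SAP 3.4 and 4.4, a man with no recorded death is censored at his last contact or last known alive date. For PSA progression, "Those subjects who do not experience PSA progression will be censored in the analysis at the date of their last PSA assessment".

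**The concern.** The result is an odd ordering. A man who withdraws all consent is traced for death every 3 months, while a man who still consents but is judged non-compliant is not. The documents give no reason for this.

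Two things are at stake. The first is information: deaths that an index look-up would find are not counted. The second is the censoring assumption. Kaplan-Meier and Cox analyses treat censoring as unrelated to prognosis, but removal for poor adherence may be linked to tolerance or decline.

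The arms also differ in how they are exposed to the compliance trigger. Protocol 5.6 checks enzalutamide compliance at every dispensing visit. By Protocol 5.3 the concurrent arm has 10 such visits, starting before the first leukapheresis, and the sequential arm has 8, starting at week 10. Discretionary removal is made with the arm known, because the trial is open-label (Protocol 5.5).

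**Working it through.** **Who is traced after leaving the study**

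| Reason for leaving | Section | SSDI/NDI tracing stated |
|---|---|---|
| Withdraws consent | 4.3.4 | Yes |
| Loses ability to consent | 4.3.4 | Yes |
| Lost to follow-up | 4.4 | Yes |
| Fails to comply | 4.3.4 | No |
| Investigator or sponsor discretion | 4.3.4 | No |
| Sponsor terminates the study | 4.3.4 | No (follow-up ends for everyone) |

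**The plan's own figures.** The documents give no event count, power or drop-out rate for overall survival or PSA progression. The only sized endpoint is the immune response. With log-scale SD = √ln(1 + 1.25²) = 0.970 and a difference of ln 2, a two-sample t calculation gives 90.6% power at 43 per arm and 69.7% at 25 per arm. This matches the stated 90% and approximately 70%. None of it bears on survival follow-up.

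**Inputs for the survival illustration**
- Median 25.8 months: sipuleucel-T arm of the pivotal trial cited in Protocol 1.1.2, used here as an assumption.
- 52 men: SAP 3.1.
- 36 months of follow-up: SAP 4.4.
- Exponential survival: assumption.

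**Expected deaths with full tracing.** h = ln 2 / 25.8 = 0.02687 per month. P(death by 36 months) = 1 − exp(−36h) = 1 − 0.380 = 0.620. Deaths = 52 × 0.620 = 32.2.

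**Cost of one untraced removal.** A man alive when removed at month u would later have been recorded as dead with probability 1 − exp(−h(36 − u)):
- u = 0: 0.62
- u = 6: 0.55
- u = 12: 0.48
- average over year 1: 0.55

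So each removal costs about 0.5 to 0.6 of a death. At the average, 2, 5 or 8 removals lose 1.1, 2.8 or 4.4 deaths, which is 3%, 9% or 14% of 32.2.

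**Effect on precision.** The removal rate is assumed, because none is given. If a share of the 52 men is scheduled for untraced removal evenly over year 1, some die first and are counted, so the loss averages 0.620 − 0.145 = 0.475 per scheduled man. The 95% half-width for the log hazard ratio is 1.96 × 2/√deaths.

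| Removed | Deaths seen | Half-width | 95% CI around HR 1 |
|---|---|---|---|
| 0% | 32.2 | 0.69 | 0.50 to 1.99 |
| 5% | 31.0 | 0.70 | 0.49 to 2.02 |
| 10% | 29.8 | 0.72 | 0.49 to 2.05 |
| 15% | 28.5 | 0.73 | 0.48 to 2.08 |
| 20% | 27.3 | 0.75 | 0.47 to 2.12 |

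**Effect on the hazard ratio.** This was simulated with a true ratio of 1. In each arm 20% of men have 2 or 3 times the hazard, and removals come only from that group, during year 1.

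| Removed, arm A v arm B | Observed HR, 2× hazard | Observed HR, 3× hazard |
|---|---|---|
| 10% v 10% | no shift | no shift |
| 10% v 0% | 0.96 | 0.94 |
| 20% v 10% | 0.95 | 0.93 |
| 20% v 0% | 0.92 | 0.89 |

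When the men removed had the same hazard as the rest, there was no shift for any split between the arms. Bias therefore needs both conditions: removal related to prognosis, and removal that differs by arm.

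**The case against.** **The plan intends to keep survival data.** SAP 4.4 says without exception that survival is followed for 3 years from randomisation. Protocol 6.6 accepts SSDI/NDI as a source for the date of death. Both disposition sections (Protocol 8.5.1, SAP 4.6.2) allow that survival status may still be obtained after other assessments are refused. This shows intent, and 4.3.4 is silent on tracing these men rather than forbidding it. But none of these places sets out tracing for the two groups, and SAP section 1 ties the 3 years to men still being followed.

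**Non-compliance may be rarer than the wording suggests.** A reader might infer that any man who skips doses or visits must leave the study. The documents do not say so: the term is undefined, Protocol 4.3.2 keeps men who stop enzalutamide in assessments or LTFU, Protocol 8.5.5 summarises percent compliance, and a man who stops responding falls under 4.4 and is traced. This stands, and it limits the likely number of removals.

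**PSA and ECOG.** A reader might infer serious damage to the PSA analysis. Table 1 footnotes i and m stop LTFU collection of ECOG status and PSA after one final value once enzalutamide ends. Keeping these men in LTFU would therefore add little for either endpoint.

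**ITT membership.** A reader might infer that men drop out of the ITT analysis. They do not; they lose follow-up only.

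**Size of bias.** One can build a case in which a true hazard ratio of 1.07 or 1.15 appears as about 1.00. It needs 10% or 20% of one arm removed at time zero, all with doubled hazard, and nobody removed from the other arm. Nothing in the documents supports those inputs.

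**Stakes.** Survival is a secondary endpoint, SAP section 4 treats all analyses as descriptive or exploratory, and the primary immune analysis in Protocol 8.3 does not use the ITT set. This stands and lowers the priority.

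**Conclusion.** The gap in the text is certain: two groups who may still be consenting leave all assessment with no stated survival tracing, while men who withdraw consent are traced. The consequence is early censoring, mainly for overall survival. Next therapy and first opioid use, both exploratory, lose follow-up too.

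The size is modest. Against about 32 expected deaths, each untraced removal in year 1 costs about 0.5 to 0.6 of a death. Even 20% removal widens the interval around a hazard ratio of 1 only from 0.50–1.99 to 0.47–2.12. These figures rest on exponential survival, the borrowed 25.8-month median and 36 months of follow-up.

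Bias in the arm comparison is possible but not shown. It requires removal that is both related to prognosis and unequal between arms, and without a removal rate it cannot be quantified. This is a cheap improvement to make, not a flaw that undermines the trial.

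**What to change.** 1. In Protocol 4.3.4, extend the 3-monthly SSDI/NDI sentence to every randomised man who is no longer in direct follow-up, whatever the reason, until the study ends.
2. State there that non-compliance or discretionary withdrawal does not by itself end LTFU contact for survival, next therapy and first opioid use, unless the man withdraws consent or the investigator withdraws him from assessment in his best interest, as Protocol 4.3 permits. Keeping that exception avoids a conflict with 4.3. Such a man would still be covered by the index look-up.
3. Leave the treatment-stopping rules unchanged.
4. In the SAP, report removals for these two reasons by arm, with timing, and add a sensitivity analysis of overall survival for informative censoring. This step can be done on existing data even if the protocol is no longer amended.

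The cost is amended wording, one disposition line, one sensitivity analysis and a few extra index look-ups or telephone calls, through a process already set up for other withdrawals.

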#### **4.4 Lost to Follow-Up**

If the subject fails to respond to requests for follow-up, the clinical trial site will send a registered letter, at a minimum, to the subject requesting contact with the clinic. All attempts to resume contact (including copies of written correspondence) will be included in the source documentation. Subjects who do not respond to requests for follow-up after all reasonable attempts to establish contact will be considered "lost to follow-up". Subjects who are lost to

follow-up will be followed by the investigator for survival every 3 months using the SSDI and the NDI. Date of death, where available, will be recorded in the subject's medical record and on the CRF.

#### **4.5 Disease Progression**

Disease progression is determined by the investigator per the definition below. The earliest date of disease progression will be recorded in the subject's medical record and on the CRF. Following disease progression, all study treatments will cease, the subject will undergo a post-treatment visit, enter LTFU, and will be treated at the investigator's discretion.

Any 1 or more of the following events constitutes disease progression:

- PSA Progression (based on Prostate Cancer Working Group 2 criteria, (Scher 2008):
  - Decline from baseline: the first PSA increase that is  $\geq 25\%$  and  $\geq 2$  ng/mL above the nadir, and which is confirmed by a second value 3 or more weeks later (i.e., a confirmed rising trend).
  - No decline from baseline: PSA progression  $\geq 25\%$  and  $\geq 2$  ng/mL after 12 weeks of enzalutamide treatment.

PSA measurements obtained during the first 12 weeks of enzalutamide treatment should not be used as the sole criterion for determining progression. Study treatments may be continued in equivocal cases where there is PSA progression but no clear evidence of disease progression or clinical deterioration, and where the investigator feels the subject is deriving clinical benefit from the study treatments and subject safety is not compromised (Scher 2008).

- Clinically significant disease-specific event:
  - New spinal cord or nerve root compression.
  - New pathologic fracture.
  - Development of metastatic disease in a new anatomic location.
  - Disease progression based on radiographic imaging and Response Evaluation Criteria in Solid Tumors criteria version 1.1.

